(a) Routine blood test: white blood cell, neutrophil, lymphocyte, neutrophil ratio, lymphocyte ratio, red blood cell, hemoglobin, platelet.

(b) Blood biochemistry: alanine aminotransferase, aspartate aminotransferase, alkaline phosphatase, lactate dehydrogenase, gamma glutamyltransferase, total bilirubin, direct bilirubin, total protein, albumin, urea, creatinine, uric acid, glucose, triglyceride, total cholesterol, potassium, sodium, chloride, calcium, phosphorus.

(c) Routine blood coagulation: prothrombin time, activated partial thromboplastin time, thrombin time, fibrinogen, prothrombin time -INR.

(8) Auxiliary examinations:

(a) Auxiliary examinations in the screening period include: BCVA OU, IOP OU, OCT of study eye, wide angle CP of study eye, the multifocal electroretinogram of study eye, microperimetry analysis of study eye, ocular axis measurement of study eye, B-scan ultrasound of study eye. Accept the examination results carried out before the informed consent signature during the same hospitalization.

(b) Auxiliary examinations in V1 and 2 include: BCVA OU, IOP OU, OCT of study eye, wide angle CP of study eye; ocular axial measurement of study eye;

(c) Auxiliary examinations in V3 include: BCVA OU, IOP OU, OCT of study eye, wide angle CP of study eye, B-scan ultrasound of study eye;

(d) Auxiliary examinations in V4 include: BCVA OU, IOP OU, OCT of study eye, wide angle CP of study eye;

(e) Auxiliary examinations in V5, 6, 7, end visits, and unscheduled visits include: BCVA OU, IOP OU, OCT of study eye, wide angle CP of study eye, the multifocal electroretinogram of study eye, microperimetry analysis of study eye and B-scan ultrasound of study eye .

(9) The low vision quality of life questionnaire: Subjects were asked to self-rate according to the low vision quality of life questionnaire (Attachment 3);

(10) Adverse events: Adverse events were collected from the time the subjects sign informed consent until the end of the study.

(11) Previous/ combined medication: Collect relevant information from the time the subjects sign informed consent until the end of the study, including all the medication used for the treatment of AE or SAE.

9. Outcome Assessment

1) Primary Outcome Assessment:

Macular hole closure rate: Fundus examination combined with optical coherence tomography (OCT) are performed 3 months after surgery.

2) Secondary Outcome Assessment:

Best corrected visual acuity (LogMAR): 6 months after the surgery

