According to randomization procedures, the researchers assign ID numbers to patients. The ID number of the randomization group must be recorded together with the patient screening number in a random directory. Completed random directory should be signed and hand over to the data center by the researcher.

Masking method

In this study, the third party independent evaluation method is used to evaluate the results of the study. The analyzer is in the masking state, and the subjects and the surgeons are in the non-masking state.

Outcome evaluation

1) Primary Outcome Measures:

To evaluate the effectiveness of different surgical procedures by evaluating the following

indicators:

The difference between macular hole closure rate, closed type in each group from baseline to the 3rd month

2) Secondary Outcome Measures:

To evaluate the effectiveness and safety of different surgical procedures by evaluating the following indicators:

The difference of the reattachment rate of retinal detachment between each group from baseline to the 6th month

The difference of the reattachment rate of retinal detachment between each group from baseline to the 12th month

The change of BCVA relative to baseline and the difference between groups from baseline to the 6th month

The change of BCVA relative to baseline and the difference between groups from baseline to the 12th month

The number of people whose BCVA result improves by more than 1 row, 2 rows and 3 rows comparing to the baseline at a time.

The number of people whose BCVA result decreases by 3 rows comparing to the baseline at a time

The difference of multifocal ERG results between each group from 1 week to the 6th month after surgery

The difference of multifocal ERG results between each group from 1 week to the 12th month after surgery

The change of microperimetry analysis results from 1 week to the 6th month after surgery relative to baseline, and the difference between each group

The change of microperimetry analysis results from 1 week to the 12th month after surgery relative to baseline, and the difference between each group

The change of the extent of foveal ellipsoid zone damage from baseline to the 6th month after the surgery relative to baseline, and the difference between each group

The change of the external limiting membrane integrity of fovea from baseline to the 6th month after the surgery relative to baseline, and the difference between each group

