The change of the extent of foveal ellipsoid zone damage from baseline to the 12th month after the surgery relative to baseline, and the difference between each group

The change of the external limiting membrane integrity of fovea from baseline to the 12th month after the surgery relative to baseline, and the difference between each group

Describe the number of retreatment and retreatment modalities for patients with different surgical procedures over a period of 12 months

Evaluate the safety of different surgical procedures by assessing the type, frequency and severity of ocular adverse events and non-ocular adverse events or severe adverse events during 12 months

Data analysis

(1) Validity analysis: Descriptive statistical method is used to describe the research indicators. Univariate analysis of continuous variables is performed using ANOVA, and univariate analysis of categorical variables is performed using chi square test. The repeated measurement data are analyzed by mixed effect model. The population of effectiveness analysis is the population of people with intention to be treated.

(2) Safety analysis: The safety assessment of clinical parameters (including adverse events, laboratory tests, vital signs, etc.) will be carried out. Descriptive statistics method is adopted. The safety analysis of the population is the population of all groups received treatment.

(3) Subgroup analysis: To determine whether the therapeutic effects of different subgroups are consistent, the component outcomes (and 95% confidence interval (CI)) are estimated for the major endpoints within the subgroup of the following categorical variables:

The type of retinal detachment [type 1 (within the arcade area), type 2 (beyond the arcade area)]

Gender (male and female)

CRC assistance

The study requires one to two clinical research coordinator (CRC)

Responsibilities:

-
- (1) Contact the subjects before 3-7 days before a follow-up;
 - (2) Communicate with the director in advance, and make appointments for patient follow-ups;
 - (3) Arrange the relevant examination for the patients;
 - (4) Have good communication skills;
 - (5) Fill in Case Report Form.

Benefit status of subjects

The therapy in this study may help to further control the patient's condition, to optimize the treatment of the disease, to provide the necessary advice for the future treatment of patients, to provide useful information for treatment or disease;

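### BCVA is a LogMAR value at 6 months in two outcome lists and a change at 6 and 12 months in a third; one baseline-adjusted model with ranked time points would settle this and usually gain precision

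*Protocol*

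**What the plan says.** **BCVA endpoint.** The protocol Summary (item 9, Outcome Assessment) and the Specific Study Protocol (Secondary Outcome Measure) both list "Best corrected visual acuity (LogMAR): 6 months after the surgery". The Specific Study Protocol's Outcome evaluation section instead lists "The change of BCVA relative to baseline and the difference between groups from baseline to the 6th month" and also "The change of BCVA relative to baseline and the difference between groups from baseline to the 12th month".

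**Method.** Summary item 14 and the Data analysis section use the same two sentences: "Univariate analysis of continuous variables is performed using ANOVA" and "The repeated measurement data are analyzed by mixed effect model". Neither names a covariate, and neither says which sentence covers BCVA.

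**Data collected.** Summary item 8, remark (8), plans BCVA at screening and at every postoperative visit. Screening also includes "the multifocal electroretinogram of study eye, microperimetry analysis of study eye, ocular axis measurement of study eye".

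**Other functional endpoints.** Outcome evaluation words multifocal ERG as "The difference of multifocal ERG results between each group from 1 week to the 6th month after surgery" and microperimetry as "The change of microperimetry analysis results from 1 week to the 6th month after surgery relative to baseline, and the difference between each group". A 12-month version of each follows. Only microperimetry is stated relative to baseline.

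**The concern.** The outcome lists differ in form (value or change) and in time points (6 months, or 6 and 12 months). With two methods on offer as well, several analyses could each be presented as the BCVA result.

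If ANOVA is used, the value and the change give treatment estimates that differ by exactly the chance difference in baseline means, which is not negligible in a trial of 38 eyes. Either analysis also usually discards precision that the screening measurement could supply at almost no cost.

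At stake are the precision and the clear reading of a secondary endpoint.

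**Working it through.** **1. Inputs from the protocol.** There is no BCVA sample size or power figure to reproduce. The only input is the trial size set for hole closure: 17 per group with 10% loss, 34 / 0.90 = 37.8, so 38 in total and 19 per arm.

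**2. Assumptions.** The protocol gives no SD, correlation or target difference for BCVA. Assumed: baseline to follow-up correlation ρ = 0.3 / 0.5 / 0.7; ratio k of follow-up SD to baseline SD from 0.7 to 1.4; for power, follow-up SD 0.5 LogMAR and a true difference of 0.3 LogMAR.

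**3. How far value and change can part.** The two estimates differ by the difference in baseline means. Its standard error at 19 per arm is √(2/19) = 0.32 baseline SDs. With a baseline SD of 0.5 LogMAR (k = 1) that is 0.16 LogMAR, about half the assumed effect.

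**4. Variance of the treatment estimate** (baseline SD = 1, n per arm):
- ANOVA on the value: k²
- ANOVA on change: k² + 1 − 2ρk
- Baseline-adjusted: k²(1 − ρ²) × [1 + 1/(2n − 4)]; the bracket is 1.029 at n = 19 and 1.033 at n = 17

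Adjusted relative to value is (1 − ρ²) × 1.029 at any k. For example, at ρ = 0.5: 0.75 × 1.029 = 0.772. Adjusted relative to change at k = 1 is 1.029 × (1 + ρ)/2.

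| n = 19 per arm | ρ 0.3 | ρ 0.5 | ρ 0.7 |
|---|---|---|---|
| Adjusted / value, any k | 0.937 | 0.772 | 0.525 |
| Adjusted / change, k = 0.7 | 0.429 | 0.479 | 0.504 |
| Adjusted / change, k = 1.0 | 0.669 | 0.772 | 0.875 |
| Adjusted / change, k = 1.4 | 0.866 | 0.970 | 1.029 |

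**5. Limits of the gain.** Against the value, the ratio reaches 1 when ρ² = 1 − 1/1.029, so ρ ≈ 0.17; below that there is no gain. The change variance equals k²(1 − ρ²) + (1 − ρk)², so adjusted relative to change can never exceed 1.029. It reaches that at k = 1/ρ (k ≈ 1.4 for ρ = 0.7). The worst loss is therefore 2.9% of variance at 19 per arm and 3.3% at 17.

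**6. Power, 17 evaluable per arm (noncentral t, two-sided 5%).** Value 40%. Change 30 / 40 / 59% at k = 1.0. Adjusted 42 / 49 / 65% at any k.

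**7. Validity.** In simulation at 17 per arm (20,000 trials per correlation, ρ from 0 to 0.7), type I error was 0.047 to 0.051 for all three analyses. None is biased on average.

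**8. What the two wordings allow.** Simulation at 19 per arm, k = 1.0, 20,000 trials per cell: value and change ANOVA disagree on significance in 8–9% of trials under no effect and in 30–40% at a true effect of 0.6 SD. Under no effect, at least one of the two is significant in about 8–10%.

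**9. What adjustment alone does not cure.** Testing the adjusted contrast at both 6 and 12 months, with a correlation of 0.8 assumed between them, gives at least one false positive in 8.2 / 8.3 / 8.9% of trials at ρ = 0.3 / 0.5 / 0.7. The time points must also be ranked.

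**10. Mixed model.** With unstructured covariance, the same 0.8 correlation, 10% missing at random before 12 months and k = 1.0 (15,000 trials), the variance with baseline relative to without is 0.934 / 0.766 / 0.518 at 6 months and 0.945 / 0.785 / 0.535 at 12 months.

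**11. Multifocal ERG and microperimetry.** Outcome evaluation starts both contrasts at 1 week. Remark (8) plans both at screening and then from V5, which the visit table puts at 8 weeks; its lists for V1 to V4 contain neither. No 1-week value is scheduled.

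**The case against.** The strongest case against is that nothing here is wrong. ANOVA is a valid test; covariates for a secondary endpoint are ordinary SAP content; and the mixed model already suits BCVA, which is measured at every visit. The shorter wording gives variable, scale and time without excluding a change score, so the lists may differ only in detail. The benefit rests on assumed correlations and can vanish.

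Much of this stands. The absence of a covariate list is not held against the protocol, and the gain is conditional, as shown. But the protocol does name a covariate-free method for continuous variables and does not say whether BCVA falls under it or under the mixed model. Its outcome lists also disagree on form and time points. An analysis plan could choose between them, but the protocol's lists would still disagree.

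Three stronger readings are tempting and not supported:
- **That ANOVA would bias the BCVA comparison or inflate its error rate.** Randomization protects both the value and the change score, and the simulated error rates confirm it.
- **That 12-month BCVA appears only in Outcome evaluation.** This is true of the outcome lists only; the visit schedule plans BCVA at the 12-month end visit.
- **That baseline adjustment by itself ends selective reporting.** It removes the choice between value and change, but the choice between 6 and 12 months carries a false-positive rate of much the same size until one is made the main contrast.

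**Conclusion.** The point holds as a matter of consistent wording and near-free precision on a secondary endpoint; it is worth changing. The primary closure analysis is not affected.

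That the lists differ, and that BCVA fits both named methods, can be read directly from the text. The size of the precision gain cannot, because it depends on a correlation and an SD ratio that the protocol does not give. Over the assumed range, adjustment saves 6% to 47% of variance against the 6-month value. Against change at equal SDs it saves 12% to 33%, and at an SD ratio of 1.4 the result runs from a 13% saving to a 3% loss. The downside is capped at about 3%.

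The 1-week start for multifocal ERG and microperimetry is a separate, definite mismatch with the visit schedule and does not depend on any assumption.

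**What to change.** **Summary item 14 and Data analysis.** State that BCVA is analysed by one model, the mixed effect model already named. Postoperative values are the response; screening BCVA and detachment type (the randomization stratum) are covariates; treatment is compared through treatment-by-visit contrasts. With screening BCVA as covariate the treatment estimate is the same for the value and for the change. ANOVA can remain for description.

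**Summary item 9, Secondary Outcome Measure and Outcome evaluation.** Word the BCVA endpoint identically. Make 6 months the main contrast, since it is the only time point in the first two lists, and 12 months supportive.

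**Multifocal ERG and microperimetry.** Use the screening value as baseline covariate, and reconcile the 1-week start in Outcome evaluation with remark (8) of the schedule.

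**Cost.** For BCVA, analysis wording and two degrees of freedom, with no new data. The baseline covariate costs at most 2.9% of variance at 19 per arm (3.3% at 17). In simulation with a non-prognostic stratum, detachment type adds about 0% if arms are balanced within strata and about 2.6% if they are not.
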